Criteria	Klinefelter syndrome or Y-chromosome microdeletions), hypogonadotropic hypogonadism (that might respond to gonadotropin injections), the use of anabolic steroids, illicit drugs, or the consumption of more than 4 alcoholic beverages daily, severe mental health problems, or current therapy with retinoic acid (e.g. Accutane) or vitamin A.

Efficacy	In this study, count of total, motile sperm after 24 weeks of
Parameters	treatment.
Safety	CBC, clinical chemistry panel (glucose, liver and renal
Parameters	function tests including urea, creatinine, albumin, alanine aminotransferase, aspartate aminotransferase, alkaline phosphatase, bilirubin), full lipid panel including Total cholesterol, HDL, LDL, triglycerides at screening and at the end of treatment. Additional measures will be conducted if any abnormal values are found until the end of study visit. • Adverse event and concomitant medications throughout the study. Other safety parameters include vital signs; and changes in pre- and post-treatment physical examination results and score on the PHQ9 depression questionnaire.
Evaluations	The following determinations will be made in all subjects: • Serum samples will be collected for the measurement of concentrations of vitamin A, all-trans and 13-cis retinoic acid, testosterone, FSH and LH will be collected before the beginning of the treatment, and monthly during treatment.
Other Assessments	Demographic characteristics, including age and race, will be collected
Statistical	The primary endpoint is the effect of treatment on the count
	of total, motile sperm between treatment groups after 24
Analysis	weeks. This analysis will be conducted using a Kruskal-Wallis ANOVA is the primary endpoint.

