This data suggests that lower intratesticular retinoic acid is associated with impaired spermatogenesis; however, it is unclear from this cross-sectional data if the low retinoic acid is a result of the infertility or a cause of it. Only an interventional trial of retinoic acid in infertile men will answer the question of the ability of retinoic acid to improve spermatogenesis in this population.

Objectives

2.1 Primary Objective:

To determine the effect of 13-cis retinoic acid administration on total motile sperm count in men with oligoasthenoteratozoospermia

2.2 Secondary Objectives:

- o To determine the chance of pregnancy during treatment with 13-cis retinoic acid
- o To determine the concentration of 13-cis retinoic acid in the seminal plasma of treated men
- o To determine the side effects and tolerability of treatment with 13-cis retinoic acid

3. Rationale, Benefits and Risks

Male infertility is common and difficult to treat unless men have an easily identified gonadotropin deficiency. Many men have idiopathic infertility. Retinoids are necessary for spermatogenesis, but no controlled studies of retinoic acid administration to men with infertility have been conducted. We have shown that men with abnormal spermatogenesis have lower than normal levels of intratesticular retinoic acid, suggesting that intratesticular retinoic acid deficiency is associated with infertility. In this study, we aim to determine if retinoic acid therapy can improve sperm counts in men with low sperm counts. The medication, 13-cis retinoic acid is widely available and prescribed for the treatment of acne, suggesting that serious adverse events, especially at the low doses to be tested are unlikely.

4. Compliance

All aspects of this study will be performed according to GCP and ICH guidelines, under an active IND.

5. Study Design

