We will conduct a prospective, three-arm, randomized, double-blinded, placebo-controlled interventional trial to determine the impact of therapy with 13-cis retinoic acid on sperm indices in infertile men. Sixty (n=20/group) infertile men with abnormal sperm analyses will be enrolled in a 24-week study of 20mg or 40 mg of 13-cis retinoic acid or matching placebo daily. The subjects will be closely followed for side effects related to treatment. The impact of treatment on indices of spermatogenesis will be determined by monthly seminal fluid analyses. All aspects of this study will be performed in compliance with Good Clinical Practice (GCP) regulations, ICH guidelines, the Declaration of Helsinki, and under an FDA Investigational New Drug (IND) application.

6. Duration of the Study

Subjects: Subjects will undergo a screening phase of up to 60 days. After fulfilling all entry criteria, the first 60 subjects will be randomly assigned to one of the three groups. The treatment phase will last for 24 weeks and subjects will have two post-treatment visits, about 4 and 12 weeks after the end of treatment.

Enrolment should be completed in approximately 12 months, resulting in total study duration of about 24 months including screening, treatment phase, end of study visit procedures, close out and data analysis.

7. Number of Subjects

60 men will participate in the study (n=20/arm)

8. Dosage and Administration

13-cis retinoic acid at 20 or 40 mg daily (purchased commercially) or matching placebo

9. Selection of Subjects

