Data analysis and Interpretation of Results: The primary endpoint is the count of total motile spermatozoa in the ejaculate at week 24 of treatment compared with baseline. Secondary endpoints include other changes in sperm quality, and any pregnancies occurring during treatment as well as the incidence of side effects. The number of total motile sperm after six months of treatment will be compared between the three groups using a Kruskal-Wallis ANOVA with a Wilcoxon rank-sum post-hoc test. The change in the total motile sperm count from baseline (a secondary endpoint) will be performed with a Wilcoxon sign-rank test. Linear regression will be performed to determine if significant relationships between baseline (or delta) retinoic concentrations and changes in sperm quality are present using STATA Version 10.0 (College Park, TX, USA). For all comparisons, an alpha of 0.05 will be considered significant.

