14.1 Sample size consideration

Inclusion of 20 men per group will allow for an 80% power to detect a greater than a 20% difference for total motile sperm count at week 24 compared with placebo with a variance of 25% and allowing for a drop-out rate of 10% at an alpha of 0.05.

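### The regression of sperm change on retinoic acid names no term for treatment arm: a pooled delta slope can be significant merely because the drug works, and the baseline slope cannot show who responds to it

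*Combined protocol and SAP*

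**What the plan says.** Section 14 (Statistical Considerations) gives this analysis one sentence: "Linear regression will be performed to determine if significant relationships between baseline (or delta) retinoic concentrations and changes in sperm quality are present". The predictor is a baseline or a change value and the outcome is a change in sperm quality. No covariate, arm term, interaction, pooling rule or within-arm rule is given there or elsewhere. The same section adds: "For all comparisons, an alpha of 0.05 will be considered significant".

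Three other places bear on how the sentence would be carried out.

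- Section 8 gives the treatments: "13-cis retinoic acid at 20 or 40 mg daily (purchased commercially) or matching placebo". The randomised drug is therefore the substance whose concentration serves as the predictor.
- The Synopsis, under Evaluations, introduces the measurements with "The following determinations will be made in all subjects" and lists "concentrations of vitamin A, all-trans and 13-cis retinoic acid, testosterone, FSH and LH will be collected before the beginning of the treatment, and monthly". Placebo men therefore have retinoid values too and can enter the regression.
- Section 1.0 says of the earlier observational study that "it is unclear from this cross-sectional data if the low retinoic acid is a result of the infertility or a cause of it", and goes on to call for an interventional trial.

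The comparison of the randomised arms is separate: a Kruskal-Wallis test on the count of total motile sperm, with rank-sum post-hoc tests.

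**The concern.** The two predictors raise different problems.

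**Delta retinoic acid.** Its variation has two sources: the differences between arms, created by randomisation to 0, 20 or 40 mg, and the differences between men within an arm. A single slope over all men mixes them. If the drug raises sperm counts by any route, men in the active arms tend to have both a larger rise in retinoic acid and a larger rise in sperm. The pooled slope is then positive even if concentration is irrelevant within each arm, and it adds little to what the arm comparison already shows.

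**Baseline retinoic acid.** This is independent of arm by randomisation, so omitting arm does not distort its slope. But a slope over placebo and active men together describes which men improve, whatever they were given. The rationale in Section 1.0 is that some infertile men may have too little retinoic acid in the testis. The natural question is then whether men with low values gain more from the drug. Only a baseline-by-treatment interaction addresses that.

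This regression is the only planned analysis that links retinoid levels to sperm response, so its wording decides what the trial can say on that link.

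**Working it through.** The plan gives no figure for this regression, so there is none to reproduce. The power statement in Section 14.1 concerns the arm comparison; only its drop-out rate is used here.

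**Inputs from the documents**
- Three arms of 20 men (Section 7) and 10% drop-out (Section 14.1): 20 × 0.90 = 18 evaluable per arm, 54 in all.
- Alpha 0.05 (Section 14). Sidedness is not stated; two-sided is assumed.

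**Assumptions, because the documents give no values**
- Drug effect E, equal in both active arms, in residual SDs of sperm change: 0, 0.4 or 0.8.
- Separation S between placebo and 40 mg in mean delta retinoic acid, in within-arm SDs: 1, 2 or 4, with 20 mg halfway.
- No link between delta and sperm change within any arm.

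**Step 1: expected pooled slope.** Arm means of delta are 0, S/2 and S; arm means of sperm change are 0, E and E.
- Between-arm variance of delta = S²/6; total variance = S²/6 + 1.
- Covariance of delta with sperm change = S·E/6.
- Expected pooled slope = (S·E/6) / (S²/6 + 1) = S·E / (S² + 6).

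For E = 0.8 this gives 0.8/7 = 0.114, 1.6/10 = 0.160 and 3.2/22 = 0.145 at S = 1, 2 and 4. The simulated means were 0.117, 0.165 and 0.148. With arm as a factor the expected slope is 0, and the simulated means were 0.000 to 0.004.

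**Step 2: how often the delta slope is significant** (4,000 simulated trials per setting, ordinary least squares)

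| Drug effect E | Separation S | No arm term | Arm as factor |
|---|---|---|---|
| 0 | 1 / 2 / 4 | 5.4% / 4.8% / 5.3% | 5.2% / 4.8% / 4.6% |
| 0.4 | 1 / 2 / 4 | 6.4% / 11.8% / 16.9% | 4.1% / 4.8% / 5.2% |
| 0.8 | 1 / 2 / 4 | 13.4% / 30.4% / 50.3% | 5.0% / 5.2% / 5.6% |

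The excess appears only if the drug works, and in these settings it grows with the separation of the arms.

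**Step 3: baseline retinoic acid.** With no true baseline relationship, the baseline slope without arm is significant in 4% to 5% of trials at every drug effect tried, so omitting arm does no harm. With a purely prognostic slope of 0.4 and no drug effect, it is significant in 79.6% of trials without arm and 77.9% with arm. The baseline-by-treatment interaction (both active arms against placebo) is significant in 4.6%. The 79.6% is power to find a true prognostic association, not an error rate. The point is that this slope does not bear on response to the drug.

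**Step 4: what the alternatives cost**
- If the effect truly runs through concentration (slope 0.2 per within-arm SD), power at S = 1, 2 and 4 is 33%, 46% and 78% without arm, and about 29% at each with arm.
- With no drug effect, S = 2, and a hidden within-arm factor acting on both delta and sperm change (path 0.4 to each), the slope is significant in 15% of trials without arm and 22% with arm.
- The interaction has 27% power for a slope difference of 0.4 and 73% for 0.8.

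**The case against.** The case on the other side is substantial, and most of it stands as a limit on the point.

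- **The plan is silent; it does not exclude arm.** A reader might infer that the model has been fixed without an arm term and will mislead. The documents do not support that. They leave the handling of arm open, and without a drug effect nothing is inflated.
- **A pooled delta slope is a real association when the drug works.** Section 14 asks only whether relationships are present. It does not call the result causal or a concentration-response finding.
- **A reader might infer that omitting arm also spoils the baseline slope.** It does not, as step 3 shows. The baseline issue is a different question left unasked.
- **A reader might infer that the regression gives up the randomised comparison.** It does not. The Kruskal-Wallis test keeps it, and that test addresses the question for which Section 1.0 wants an interventional trial.
- **The analysis is not a test of the deficiency hypothesis.** That hypothesis concerns retinoic acid inside the testis. The trial measures serum and plans seminal plasma, and no objective in Section 2 is mechanistic. No choice of model would settle cause and effect.
- **Adjusting for arm is not plainly better.** It discards the randomised variation, loses power if concentration mediates the effect, and leaves within-arm confounding untouched.

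The last item argues for reporting both slopes, not for leaving the model unstated. What remains is that the sentence, carried out literally, gives one slope that a reader cannot interpret, and that the choice of model is left open until the data are unblinded.

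**Conclusion.** The point holds as a gap in specification, of minor severity. Section 14 names no arm term, interaction or baseline sperm count. Run over all men as written, the delta slope is significant in about 6% to 50% of trials with no within-arm link, against about 5% with arm in the model. That range rests on assumed drug effects of 0.4 to 0.8 SD, assumed separations of 1 to 4 within-arm SDs and 18 evaluable men per arm. The 50% belongs only to the largest effect and widest separation tried and should not be quoted alone.

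Separately, the baseline slope is unbiased by the omission, but it measures prognosis and cannot show whether men with low retinoic acid respond better to the drug.

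The primary comparison is unaffected, and the regression is not among the secondary endpoints listed in Section 14.

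**What to change.** Replace the sentence in Section 14 with a short specification.

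1. **Delta retinoic acid:** report the slope with arm as a factor, or slopes within each arm, beside the pooled slope. Label both as associations.
2. **Baseline retinoic acid:** fit baseline, treatment and their interaction, and report the interaction as the test of differential response.
3. **All models:** include baseline sperm count. Men enter on low counts, so some regression to the mean in the change score is likely. Section 1.0 also reports lower retinoic acid in the testis where sperm quality is poor, so baseline retinoic acid may carry part of that effect. This was not quantified here.
4. Name the retinoid used, since several are measured, and whether it is from serum or seminal plasma.

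The cost is a few sentences and no new data; the week 0 semen sample is already planned (Section 12.4.1). Serum for retinoic acid is frozen for assay at the end of the study (Section 12.2), so the models can be fixed before those results exist.

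The plan should also state the downsides. The arm-adjusted slope loses power if the effect runs through concentration, and it stays open to within-arm confounding. Interaction power is low with about 18 men per arm, so a null result would be inconclusive.

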14.1 Sample size consideration

Inclusion of 20 men per group will allow for an 80% power to detect a greater than a 20% difference for total motile sperm count at week 24 compared with placebo with a variance of 25% and allowing for a drop-out rate of 10% at an alpha of 0.05.

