12.4.3 Visit 8 and 9 (Follow-up Visits)

The following will be done at this visit:

- Vital signs (pulse, blood pressure and respiratory rate) will be taken and recorded.
- The subject will complete the behaviour questionnaire
- Subjects will be questioned regarding concomitant medications and adverse events.
- A blood sample will be drawn for the measurement of serum FSH, LH, T, and retinoids.
- A semen sample will be obtained for the measurement of sperm count, concentration, motility and morphology

13. Study Withdrawals

Subjects withdrawing from the study can be replaced only if the withdrawal occurs before the start of the treatment. Subjects who have had medication will not be replaced, regardless of the reason for discontinuation. All efforts should be made to contact any subject who decides to discontinue study participation for the end of study safety procedures (Visit 9). The necessary clinical and laboratory examinations planned at the last visit should be performed at the end of the study whenever it occurs. The reasons for discontinuation will be documented.

Post-Admission Withdrawal Criteria

Subjects may be discontinued prematurely for any of the following reasons:

• Emergence of a severe condition(s) such that, in the judgment of the investigator, continuation in the trial would negatively impact the health of the subject.

- Personal reasons (e.g. withdrawn consent).
- Subject lost to follow-up

All subjects in a treatment arm may be discontinued prematurely if greater than 25% of the subjects in an arm are discontinued for the emergence of the same severe condition that requires individual subjects to be discontinued.

14. Statistical Considerations

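### Section 14.1 claims 80% power for a 20% difference, but on the usual reading of its inputs the planned unadjusted comparison has about 62%

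*Combined protocol and SAP*

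**What the plan says.** Section 14.1 gives the whole sample-size argument in one sentence. It claims that "Inclusion of 20 men per group will allow for an 80% power to detect a greater than a 20% difference" in week-24 total motile sperm count against placebo, "with a variance of 25% and allowing for a drop-out rate of 10% at an alpha of 0.05". It does not say whether the 25% is a variance, an SD or a coefficient of variation (CV), whether alpha is one- or two-sided, or which test was used for the calculation.

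Three other places bear on it:

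- Section 13 (Study Withdrawals): "Subjects who have had medication will not be replaced, regardless of the reason for discontinuation". Losses after the first dose therefore reduce the evaluable number.
- Section 14: week-24 counts are "compared between the three groups using a Kruskal-Wallis ANOVA with a Wilcoxon rank-sum post-hoc test". No baseline covariate is planned, and the test of change from baseline is labelled secondary. The Synopsis also names Kruskal-Wallis for the primary analysis.
- Section 14, on significance: "For all comparisons, an alpha of 0.05 will be considered significant".

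**The concern.** A standardised difference of 20/25 = 0.8 normally needs about 25 evaluable men per arm for 80% power at two-sided 0.05. The plan has 20 enrolled and 18 after its own drop-out allowance. The stated power therefore looked too high for the planned test, even before drop-out.

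This sentence is the only justification for 20 men per arm. If it is wrong, a non-significant result will be over-read: readers will believe a true 20% difference had a 20% chance of being missed when the chance was considerably larger.

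**Working it through.** **Inputs from the documents.** 20 enrolled per arm; 20% difference versus placebo; 25% variability; 10% drop-out; alpha 0.05 (all Section 14.1). Treated men are not replaced (Section 13), so evaluable n = 20 × 0.9 = 18 per arm. Unadjusted Kruskal-Wallis, then Wilcoxon rank-sum (Section 14).

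**Assumptions, because the documents are silent.** Normal data; common SD equal to 25% of the placebo mean, so d = 20/25 = 0.8; two-sided alpha as the main case, with one-sided also shown. The dose patterns for Kruskal-Wallis are assumed too.

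**Step 1: try to reproduce 80%.** Normal approximation: power = Φ(d√(n/2) − z).

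- n = 18, two-sided: 0.8 × √9 = 2.40; Φ(2.40 − 1.96) = 67.0%.
- n = 18, one-sided: Φ(2.40 − 1.645) = 77.5%.
- n = 20, two-sided: 0.8 × √10 = 2.53; Φ(2.53 − 1.96) = 71.6%.
- n = 20, one-sided: Φ(2.53 − 1.645) = 81.2%.

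Only the one-sided calculation with no drop-out comes near 80% (79.9% by noncentral t). That may be where the figure came from, but it leaves out the drop-out that the sentence says it allows for.

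**Step 2: power of the planned tests at a 20% difference.** The t-test row is noncentral t and is given for reference. The rank tests were simulated with 200,000 replicates. Wilcoxon ranges run from the exact or continuity-corrected version to the uncorrected normal approximation.

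| Test | 18 per arm, two-sided | 20 per arm, two-sided | 18 per arm, one-sided |
|---|---|---|---|
| t-test | 64.5% | 69.3% | 76.0% |
| Wilcoxon, one dose vs placebo | 61–63% | 67% | 74–75% |
| Kruskal-Wallis, both doses full effect | 64% | 69% | no one-sided form |
| Kruskal-Wallis, lower dose half effect | 51% | 56% | no one-sided form |
| Kruskal-Wallis, one dose only | 64% | 69% | no one-sided form |

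Two-sided, the shortfall is present before any drop-out. Drop-out is decisive only for a one-sided t-test (79.9% at 20 per arm, 76.0% at 18).

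**Step 3: other readings of the 25%** (18 per arm, two-sided, 20% increase).

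- CV of 25% within each arm (SD = 0.25 × that arm's mean): Wilcoxon 53–54%; Kruskal-Wallis 43–55%.
- Log scale with CV 25% (log-SD 0.246) and ratio 1.20: t-test 57.9%; Wilcoxon 55–56%.
- Literal variance of 0.25, so SD 50% and d = 0.4: t-test 21%; Wilcoxon 20–21%.

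**Step 4: what the design can detect with 80% power** (18 per arm, two-sided).

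- Common SD: about 24% by t-test. For Wilcoxon, power is 79–80% at a 24.5% difference and 80–81% at 25%.
- CV within each arm: Wilcoxon gives 70–71% at 25% and reaches 80% at about 29%.

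**Step 5: n for 80% at a 20% difference** (common SD, two-sided). The normal approximation needs 25 evaluable per arm, and 25/0.9 = 27.8, so 28 enrolled. The t-test needs 26 evaluable, and 26/0.9 = 28.9, so 29 enrolled.

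**The case against.** The strongest reply is that the inputs are undefined, so no single figure can be called the true power. That stands in part. The 62% is conditional on the 25% being a common SD and on a two-sided test. But the other readings in Step 3 give lower power, so the ambiguity does not support 80%. Reading the 25% as 25 squared percentage points (SD 5%) would give power near 100%, but that spread is implausible for sperm counts in men admitted at any value below 10 million.

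Section 14.2 speaks of an increase, which makes a one-sided calculation arguable. Power at 18 per arm is then 74–76%, so the gap narrows but does not close.

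Some readings do reach 80%, or nearly:

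- **Success on either dose.** With unadjusted two-sided Wilcoxon tests and both doses at full effect, power is about 78–79% at 18 per arm and 82% at 20. It is about 65% at 18 if only one dose works or the lower dose has half the effect. If a significant Kruskal-Wallis test is required first, the 18-per-arm figures are about 64% (both doses), 55% (one dose) and 50% (lower dose half effect).
- **Pooling both doses against placebo** (36 versus 18): 79.1% by normal approximation, 77.6% by t-test.
- **A ratio of 1.25 on the log scale, one-sided**, at 18 per arm: t-test 84.6%, Wilcoxon 82–83%.
- **Baseline adjustment** at 18 per arm, with an assumed correlation of about 0.56 (two-sided) or 0.33 (one-sided).

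Section 14.1 describes none of these, and pooling and adjustment are not in the planned analysis.

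It can also be said that the text claims power for differences greater than 20%. A quoted power should hold at the threshold named, and here 80% begins at about 24–25%. Finally, the Synopsis calls this a pilot. That is a good reason not to demand more men, but the protocol still makes a numerical power claim, and it should be correct.

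**Conclusion.** The concern holds. For the unadjusted comparison that the protocol plans, 20 men per arm with 10% drop-out do not give 80% power for a 20% difference. With 18 evaluable per arm, two-sided alpha 0.05, normal data and a common SD of 25% of the placebo mean, power is about 62% (Wilcoxon, one dose versus placebo) and 51–64% (Kruskal-Wallis). A true 20% difference would be missed by that Wilcoxon test in about 38% of trials (100 − 62), against the 20% that the text implies.

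The exact size depends on what the sponsor meant by the 25% and on sidedness. That no two-sided, unadjusted, single-dose comparison reaches 80% at d = 0.8 with 18 or 20 per arm does not. This should be fixed, but it does not threaten the conduct of a pilot trial.

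**What to change.** Keep 20 men per arm and the planned analysis. In Section 14.1, have the sponsor define the 25% as an SD or a CV and give its source, and state the sidedness, the test and the evaluable number. Then restate the power to match.

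If the 25% is a common SD, suitable wording would be: *With 18 evaluable men per arm (20 less 10% drop-out), two-sided alpha 0.05, normal data and a common SD equal to 25% of the placebo mean, the Wilcoxon rank-sum test of one dose versus placebo has about 62% power for a 20% difference and 80% power for a difference of about 25%; the three-group Kruskal-Wallis test has about 51–64% power for a 20% difference, depending on the dose pattern.*

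If it is a CV within each arm, the figures become: Wilcoxon about 53–54% for a 20% increase, 70–71% for 25%, and 80% at about 29%; Kruskal-Wallis about 43–55% for 20%. Any other definition needs its own calculation.

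The cost is protocol wording only: no extra men and no change to the analysis. The one drawback is a less favourable stated power.
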